ANNEX 2. ENCEPP CHECKLIST FOR STUDY PROTOCOLS

As attached.

ANNEX 3. ADDITIONAL INFORMATION

None.

4 LIST OF ABBREVIATIONS AND DEFINITION OF TERMS

Ab	Antibody
ADR	Adverse Drug Reaction
AE	Adverse Event
ALAT	Latin American Thoracic Association
ATS	American Thoracic Society
BMI	Body Mass Index
c-ANCA	Cytoplasmic Anti-Neutrophil Cytoplasmic Antibodies
CAT	COPD Assessment Test
CK	Creatine Kinase
CRF	Case Report Form
CRP	C-Reactive Protein
CRO	Contract Research Organization
CSR	Clinical Study Report
CVD	Cardio-Vascular Disease
DLco	Diffusing capacity of the Lungs for Carbon monoxide
DM	Diabetes Mellitus
DVP	Data Validation Plan
ERS	European Respiratory Society
FBC	
FGF	Fibroblast Growth Factor
FVC	Forced Vital Capacity
GCP	Good Clinical Practice
Hb	Hemoglobin
Hct	Hematocrit
HRCT	High-Resolution Computed Tomography
IC	Inspiratory Capacity

ICH	International Conference on Harmonization
ILD	Interstitial Lung Disease
IPF	Idiopathic Pulmonary Fibrosis
IRB	Institutional Review Board
JRS	Japanese Respiratory Society
MDT	Multidisciplinary Team
MedDRA	Medical Dictionary for Regulatory Activities
p-ANCA	Perinuclear Anti-Neutrophil Cytoplasmic Antibody
PDGF	Platelet Derived Growth Factor
PI	Principal Investigator
PT	Preferred Term
RBC	Red Blood Cell
SAE	Serious Adverse Event
SAS	Statistical Analysis System®
SGRQ	St George's Respiratory Questionnaire
SOC	System Organ Class
SOP	Standard Operating Procedure
TLC	Total Lung Capacity
UIP	Usual Interstitial Pneumonia
VEGF	Vascular Endothelial Growth Factor
WBC	White Blood Cell
6MWT	Six-Minutes Walking Test

5 INTRODUCTION

This Statistical Analysis Plan (SAP) is based on the final protocol 1199-0303 dated 10 April 2017 (version 5.0) and the protocol administrative memorandums that have been approved by Institutional Review Board (IRB). The SAP provides details on the planned statistical methodology for analysis of the study data, and also outlines the statistical programming specifications for the table. It describes the safety variables, anticipated data transformations, manipulations, coding, and other details of the analyses not provided in the study protocol. A detailed description of the planned table and figures to be presented in the clinical study report (CSR). This SAP only covers the planned analysis of all safety and efficacy data collected on paper CRFs.

This SAP is written with consideration of the recommendations outlined in the International Conference on Harmonisation (ICH) E9 guideline entitled, "Guidance for Industry: Statistical Principles for Clinical Trials" and the ICH E3 guideline entitled, "Guidance for Industry: Structure and Content of Clinical Study Reports".

6 STUDY OBJECTIVES AND ENDPOINTS

6.1 Study Objectives

6.1.1 Primary Objective(s)

The primary objective is to characterize the IPF population in Taiwan with regard to their clinical course under clinical practice conditions in Taiwan.

6.1.2 Secondary Objectives

The secondary objectives are to understand the clinical characteristics and quality of life of IPF population in Taiwan.

6.2 Endpoints

Key study outcomes are to characterize lung function profile of IPF patients in clinical practice.

6.2.1 Primary Endpoint(s)

- Annual percentage of decline from baseline in FVC
- Annual decline from baseline in DLco
- Annual decline from baseline in resting and exercise SpO₂
- Annual percentage of decline from baseline in TLC
- Annual percentage of decline from baseline in IC

6.2.2 Secondary Endpoints

- Time to first acute exacerbation of IPF after enrolment
- Annual change from baseline in SGRQ
- Annual change from baseline in CAT
- Annual change from baseline in 6MWT
- Mortality (with cause of death) and time to death

6.2.3 Safety Endpoints

- Frequency of adverse events and serious adverse events.

7 STUDY METHOD

7.1 Overall Study Design and Plan

This is a non-interventional, multi-center study to collect data from patients with idiopathic pulmonary fibrosis (IPF) in clinical practice in Taiwan. The study will be carried out at 10 medical centers, the expert centers where IPF patients are mainly managed in Taiwan. A total of 100 IPF patients are planned to be included. Only patients who meet all study criteria will be enrolled.

The study duration consists of a 1-year enrolment period and a 2-year follow-up period. IPF patients will be enrolled in a consecutive manner. The observation period was from study inclusion until death, lung transplantation, end of data collection at 2-years, or loss to follow-up. Data collection will be started at the initial screening assessment based on the medical records, and prospectively thereafter if patients are eligible for inclusion.

The study will not interfere with the management of patients by their physician. Visits will be in accordance with clinical needs judged by physicians. All the data will be collected in line with real-world clinical practice (baseline [study enrolment], the first month, and every 3 months afterward).

7.1.1 Schedule of Assessments

The collection of patient data should be managed during routine clinical practice visits, which is approximately every 3 month in Taiwan. Information on pre-specified variables of interest will be collected at inclusion (baseline visit) and captured at pre-defined intervals during the follow-up period (e.g. at 3, 6 months (time window: ± 1 month) and then every 6 months (time window: ± 2 month) intervals until finalization of the study).

Variables	Week#	Baseline	Wk 4	Wk 16	Wk 28	Wk 40	Wk 52	Wk 64	Wk 76	Wk 88	Wk 100
	Visit	1	2	3	4	5	6	7	8	9	10
				← 3-month interval →							
Allowed window			± 14 days	← ± 1 month →							
Informed consent		X									
Inclusion/exclusion		X									
Demographics ¹		X									

CONFIDENTIAL
PROTOCOL NO.: 1199-0303

Variables	Week# Visit	Baseline	Wk 4	Wk 16	Wk 28	Wk 40	Wk 52	Wk 64	Wk 76	Wk 88	Wk 100
		1	2	3	4	5	6	7	8	9	10
				← 3-month interval →							
Allowed window			± 14 days	← ± 1 month →							
IPF characteristics (diagnosis)*, 2	X										
IPF symptoms ³	X	X	X	X	X	X	X	X	X	X	X
Smoking status	X										
Comorbidities	X										
- STOP-Bang Scoring Model ⁴	X ^{&}										
- Berlin Questionnaire-obstructive sleep apnea ⁴	X ^{&}				X		X		X		X
- Echocardiography data-PH	X ^{&}				X		X		X		X
Concomitant medications ⁵	X	X	X	X	x	x	X	X	X	X	X
Record of anti-fibrotic drugs*	X ⁶	X	X	X	X	X	X	X	X	X	X
Lung function*, 7	X ^{&}	X	X	X	X	X	X	X	X	X	X
6MWT*	X ^{&}						X				X
SGRQ*	X ^{&}	X	X	X	X	X	X	X	X	X	X
CAT*	X ^{&}	X	X	X	X	X	X	X	X	X	X
Acute exacerbation	X	X	X	X	X	X	X	X	X	X	X
Safety reporting ⁸		← →									
Serological tests*, 9	X ^{&}		X				X		X		X
Biomarkers*, 10	X						X				X
Gene test*, 11	X										

*Data will be collected, if applicable. All examinations and managements will be based on the discretion of the physician and regular practice.

#Data collection time points will follow visit schedule in clinical practice.

&Since this is an observational study, examinations and tests will be performed as judged appropriately by the treating physician according to local medical standards, and the results of interest that closest to the baseline will be registered only if

Variables	Week# Visit	Baseline	Wk 4	Wk 16	Wk 28	Wk 40	Wk 52	Wk 64	Wk 76	Wk 88	Wk 100	
		1	2	3	4	5	6	7	8	9	10	
				← 3-month interval →								
Allowed window			± 14 days	← ± 1 month →								

those are available prior to baseline visit.

1. Age, gender, race, education level, environmental/occupation exposures, height, weight, and BMI.
2. HRCT, surgical lung biopsy, multidisciplinary team (MDT) diagnosis, and UIP pattern.
3. Cough, dyspnea, fatigue, weight loss, dizziness, chest pain, anxiety, aching muscles and joints, clubbed fingers, require oxygen therapy (device), or others (according to physicians' judgment and should be specified on the CRF)
4. STOP-Bang Scoring Model data will be collected to assess if patients have obstructive sleep apnea, and Berlin questionnaire results will only be collected from those with suspected/confirmed obstructive sleep apnea according to STOP-Bang Scoring Model.
5. Concomitant medications used for treating comorbidities within 6 months prior to enrolment will be collected.
6. Anti-fibrotic drugs (i.e., nintedanib and pirfenidone) used within 6 months before baseline will be recorded.
7. Spirometry data include FVC, DLCO, SpO₂, TLC, IC, etc.
8. OFEV relevant ADR (serious and non-serious), fatal AEs, and pregnancies.
9. Hct, Hb, platelets, RBC, WBC, neutrophils, lymphocytes, monocytes, eosinophils, basophils, CRP, CK, rheumatoid factor, antinuclear Ab, anti-Jo1 Ab, Sjogrens SS-A or SS-B Ab, scleroderma-70 Ab, c-ANCA, and p-ANCA, etc..
10. PDGF, VEGF, FGF, etc..
11. MUC5B, etc..

7.2 Selection of Population and Inclusion/Exclusion Criteria

7.2.1 Inclusion Criteria

1. Newly diagnosed IPF within 6 months based upon recent ATS/ERS/JRS/ALAT IPF guideline (Ref 1, Raghu G, et al 2011)
 - Exclusion of other known causes of ILD (e.g. domestic and occupational environmental exposures, connective tissue disease, and drug toxicity) which needs serological test.
 - Assessment of IPF based on HRCT or HRCT and surgical lung biopsy, if available.
2. Patient ≥ 20 years of age
3. Written informed consent prior to participation

4. Patients with further follow-up possible with participating physician during planned study period
5. Ability to read and write in the local language

7.2.2 Exclusion Criteria

1. Lung transplantation expected within next 6 months.
2. Inclusion in ongoing clinical trials

7.3 Randomization and Blinding

This is a non-interventional and observational study. No randomization and blinding in this study.

7.4 Sample Size

Approximately 100 patients are planned to be enrolled based on the recruitment timeframe and patient pool in 10 medical centers, the expert centers where patients are mainly managed in Taiwan. Since most outcomes are continuous, this number should be sufficient in order to get insights into Taiwanese IPF patients.

8 GENERAL CONSIDERATIONS

8.1 Relevant SOPs and Policies

The data will be managed with data verification, data validation, data clarification, data clean, and data lock processes. The statistical analysis method should follow the statistical analysis plan before implementing the data lock procedure. All processes will follow the SOPs below:

DM 1709	Data Entry Procedure
DM 1710	Data Verification Procedure
DM 1711	Data Validation Procedure
DM 1712	Data Clarification Procedure
DM 1713	Data Lock Procedure
DM 1719	Statistical Analysis Plan Procedure
DM 1720	Statistical Analysis Report Procedure

8.2 Timing of Analyses

The final analysis will take place when all enrolled patients complete the study or permanently discontinued from the study. After the relevant data management processes are completed and data clean status is claimed, the database will be locked. The final analysis will be conducted based on the lock data.

8.3 Analysis Populations

The main analysis population will consist of all eligible patients (i.e. all patients who have signed the informed consent and fulfilled all inclusion criteria and no exclusion criteria)

8.4 Covariates and Subgroups

Subgroup analysis will be conducted based on the prescription of nintedanib and pirfenidone. All enrolled subjects will be grouped as “no anti-fibrotic drugs” and “with anti-fibrotic drugs”. Subject had no record of anti-fibrotic drugs during the observation will be categorized as “no anti-fibrotic drug”. In contrast, the subjects with at least one record of anti-fibrotic drugs will be categorized as “with anti-fibrotic drugs”.

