9.2.3 Study visits

The collection of patient data should be managed during routine clinical practice visits, which is approximately every 3 month in Taiwan Information on pre-specified variables of interest will be collected at inclusion (baseline visit) and captured at pre-defined intervals during the follow-up period (e.g. at 3, 6 months (time window: \pm 1 month) and then every 6 months (time window: \pm 2 month) intervals until finalization of the study).

Data will be collected and recorded on the CRF at baseline and follow-up visits according to **Table 1 Data Collection Schedule**, if available.

Baseline visit (Visit 1)

Non-interventional Study Protocol

BI Study Number 1199-0303

c16462309-02

Proprietary confidential information © 2017 Boehringer Ingelheim International GmbH or one or more of its affiliated companies

No data collection for study purposes must be performed unless the patient has consented to participate in the study. Once the patient has signed the informed consent form, the patient is considered to be enrolled in the study and patient details should be recorded on the enrolment log.

The following procedures will be performed at the baseline visit, and data will be collected from the medical chart and recorded on the CRF, **if available**:

- Sign informed consent form. A copy of the consent should be given to the patient.
- Review of inclusion and exclusion criteria, and record date of inclusion
- Collection of demographic data: Age, gender, race, education level, environmental/occupation exposures, height, weight, and BMI
- Collection of IPF-related characteristics: High-resolution computed tomography (HRCT), surgical lung biopsy, multidisciplinary team (MDT) diagnosis, and UIP pattern
- Record of IPF symptoms at baseline
- Record of smoking status
- Collection of comorbidities and its related concomitant medications that prescribed within 6 months prior to enrolment with IPF diagnosis.
 - Collect STOP-Bang Scoring Model results to evaluate if patients have comorbidity of obstructive sleep apnea
 - Collect Berlin questionnaire results for patients with comorbidity of obstructive sleep apnea
 - Collect echocardiography results for patients with comorbidity of PH
- Record of anti-fibrotic drugs used currently and within 6 months before enrollment with IPF diagnosis (i.e., nintedanib and pirfenidone)
- Collect spirometry results that closest to the baseline
- Collect 6MWT results that closest to the baseline

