9.9 LIMITATIONS OF THE RESEARCH METHODS

Data collection

A non-interventional study is the most suitable design for obtaining information about the use of medicines in everyday therapeutic practice and thus for clarifying prospectively questions in everyday therapeutic practice. In addition, the observational design intends to collect available data that are recorded on medical charts. The lack of data of interest may be one of the limitations.

Missing data will be handled for primary and secondary outcomes as appropriate on a case-by-case basis, depending on the extent and distribution of missing values (see Section 9.7.4). All efforts will be made to minimize missing data and loss to follow-up in patients who are enrolled. For instance, before start of data collection, a study initiation visit will be performed for each medical center, where investigators and site staffs will be trained for study implementation, data collection, and safety reporting, etc. Investigator and site staff should escalate issues that can potentially jeopardize study outcomes to sponsor or CRO upon awareness. Sponsor, CRO, and site should work closely to manage any risks.

Selection bias

The entry criteria are non-restrictive and will permit the enrolment of a broad patient population. The choice of treatment is at the discretion of the investigator. Selection bias could occur at both the site (physician) level and the patient level. To minimize the site level selection bias, the goal is to have participating centers (i.e., medical center of Taiwan) that are representative for managing IPF patients in Taiwan and have access to all available treatment options for IPF that are approved for use in Taiwan.

Selection bias at the patient level could occur if sites preferentially enroll specific patients into the study. To minimize selection bias at the patient level, consecutive enrolment is performed.

Small sample size

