The limitations created by a small sample size can have profound effects on the outcome and worth of a study. A small sample size may increase the data variability and have extremely detrimental effects. Therefore, when looking into the study outcome, study statisticians will determine whether the small sample size limitations will have a negative impact on study's results before getting underway; and if it does, study statisticians will not perform stratified analyses. Also, study results will be elaborated carefully because a small sample size may deviate the true results of the real-world population.

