8.7 Adjustments for Multiplicity

The study was not aimed to show significant difference between treatment groups and no hypothesis testing will be performed. Hence there is no need to adjust for multiplicity.

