9 SUMMARY OF STUDY DATA

All the statistical analysis will be performed and categorized by the subgroup of with anti-fibrotic drug and no anti-fibrotic drug. The summary tables will be tabulated with columns of the two subgroups. The relevant population size will be annotated in the tables.

Continuous variables will be summarized by descriptive statistics: number of observations, mean, median, standard deviation, range, and 95% confidence interval. Frequency counts and percentages of observed levels will be reported for categorical variables. The denominator of percentages will be the number of subjects with valid assessment results. Subjects with missing data will not be included in the number of denominator.

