10.3 Secondary Endpoints

- Time to first acute exacerbation of IPF after enrolment

Time to first acute exacerbation starts from the date of informed consent to the date of first acute exacerbation recorded on the CRF. Subject with exacerbation free at the time of the last contact will be censored. The time of censored is from the date of consent to the last valid date of last known date subject took anti-fibrotic drugs, date of last contact, and last visit date.

- Annual change from baseline in SGRQ

Descriptive statistics including Number, Mean±SD, Median, Range and 95% C.I. will be presented. Annual change from baseline in SGRQ will be calculated as

$$\text{Annual change from baseline} = \frac{\text{SGRQ}_{\text{follow-up}} - \text{SGRQ}_{\text{baseline}}}{\text{Days of follow-up}} \times 365.25$$

In addition to the annual change from baseline, the mean value and mean change from baseline will also be calculated.

- Annual change from baseline in CAT

Descriptive statistics including Number, Mean±SD, Median, Range and 95% C.I. will be presented. Annual change from baseline in CAT will be calculated as

$$\text{Annual change from baseline} = \frac{\text{CAT}_{\text{follow-up}} - \text{CAT}_{\text{baseline}}}{\text{Days of follow-up}} \times 365.25$$

In addition to the annual change from baseline, the mean value and mean change from baseline will also be calculated.

- Annual change from baseline in 6MWT

Descriptive statistics including Number, Mean±SD, Median, Range and 95% C.I. will be presented. Annual change from baseline in 6MWT will be calculated as

$$\text{Annual change from baseline} = \frac{6\text{MWT}_{\text{follow-up}} - 6\text{MWT}_{\text{baseline}}}{\text{Days of follow-up}} \times 365.25$$

In addition to the annual change from baseline, the mean value and mean change from baseline will also be calculated.

- Mortality (with cause of death) and time to death

Time to death is calculated from the date of consent to the date of death from any cause. Subjects with no documented death will be censored. The time of censored is from the date of consent to the last valid date of last known date subject took anti-fibrotic drugs, date of last contact, and last visit date.

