11.4 Secondary Endpoint Analyses

Time to first acute exacerbation of IPF, and time to death will be analyzed by Kaplan-Meier survival method. The graph of KM curve will be reported and summary statistics including survival estimate (25%, 50%, 75%) and 95% CI for the estimate will be tabulated.

The same analysis procedure of primary endpoints will be applied to the secondary outcomes of annual change, from baseline in SGRQ, CAT and 6MWT. The shapiro-wilk test will be performed to test the normality. Paired t-test will be used if normally distributed. Otherwise, Wilcoxon sign rank test will be adopted to conduct

the test. The sas procedure used for the tests is listed as follow.

Statistical Test	SAS procedures and option
Shapiro-Wilk test	PROC UNIVARIATE NORMALTEST
T-test	PROC UNIVARIATE MU0=0 ALPHA=0.05
Wilcoxon sign rank test	PROC UNIVARIATE MU0=0 ALPHA=0.05

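### Kaplan-Meier time to death from consent, split by any anti-fibrotic record during follow-up, builds immortal time into the drug column

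*SAP*

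**What the plan says.** - SAP 8.4 defines the no-drug subgroup over the whole observation period: "Subject had no record of anti-fibrotic drugs during the observation will be categorized as" that group. One record at any time places a patient in the drug group.
- SAP 9 makes the split general: "All the statistical analysis will be performed and categorized by the subgroup of with anti-fibrotic drug and no anti-fibrotic drug". Tables carry one column per subgroup.
- SAP 10.3 sets time zero: "Time to death is calculated from the date of consent to the date of death from any cause".
- SAP 11.4 sets the method: "Time to first acute exacerbation of IPF, and time to death will be analyzed by Kaplan-Meier survival method", with curves, quartiles and 95% confidence intervals.
- Neither document gives a landmark, delayed-entry or time-varying rule.
- First use can precede or follow consent. At baseline the protocol (9.2.3) asks for "Record of anti-fibrotic drugs used currently and within 6 months before enrollment with IPF diagnosis", and use is recorded again at each visit to Week 100. Start and end dates are collected (Protocol 9.3.1).
- On who is treated, Protocol 9.9 says: "The choice of treatment is at the discretion of the investigator".
- On purpose, SAP 8.7 says: "The study was not aimed to show significant difference between treatment groups".
- On small numbers, Protocol 9.9 asks whether the sample size would harm the results and adds: "if it does, study statisticians will not perform stratified analyses". SAP 8.4 and 9 commit to the split without that condition.

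**The concern.** For anyone not on drug at consent, subgroup membership is known only from later follow-up, yet both survival curves start at consent. A patient who first takes a drug at month 8 cannot, by construction, die in the drug column during the first 8 months. A patient who dies at month 7, before a start that might have come, is counted as no drug. The rule lengthens survival in one column and shortens it in the other even if the drug does nothing, and a larger sample would not cure it.

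What is at stake is a side-by-side display of mortality, a named secondary endpoint, in treated and untreated patients. The sponsor markets one of the two drugs, and the results are to be submitted for publication (Protocol 12). A reader would naturally take the gap between the curves as informative about treatment.

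**Working it through.** The documents give no figure for subgroup survival, so there is none to reproduce. The check asks what the planned display would show if the drug had no effect.

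**Inputs from the documents**
- Follow-up: overall survival is censored at 100 weeks (Protocol 9.7.1), so τ = 700/365.25 = 1.916 years.
- Median survival: 0.9 year (Taiwan) and 3 years (general), Protocol 7. Both run from diagnosis.
- Sample size: about 100 (SAP 7.4).

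**Assumptions**
- Those medians apply from consent and survival is exponential, so λ = ln 2/median = 0.7702 or 0.2310 per year.
- A share p is on drug at consent, and the rest start at rate s per year. The documents give neither, so a range is shown.

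**Formulas**, per enrolled patient, with k = λ + s:
- No-drug column deaths: D0 = (1−p)(λ/k)(1−e^(−kτ))
- No-drug column time: T0 = (1−p){λ[(1−e^(−kτ))/k² − τe^(−kτ)/k] + τe^(−kτ)}
- Whole cohort: D = 1−e^(−λτ), T = D/λ
- Drug column: D1 = D−D0, T1 = T−T0
- Ratio = (D1/T1)/(D0/T0)

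**Worked case** (median 0.9 year, p = 0.5, s = 0.2, k = 0.9702)
- D0 = 0.3351 and T0 = 0.3762, a rate of 0.891.
- D = 0.7715 and T = 1.0017, so D1 = 0.4364 and T1 = 0.6255, a rate of 0.698.
- Ratio = 0.698/0.891 = 0.78, although every patient has the same true rate of 0.770.
- Now move time before first dose to no drug. No-drug time becomes (1−p)(1−e^(−kτ))/k = 0.4351, and drug time 1.0017 − 0.4351 = 0.5666. The rates are 0.3351/0.4351 = 0.770 and 0.4364/0.5666 = 0.770, a ratio of 1.00.

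**Range, no confounding.** The share of the drug column that started late is [(1−p)(s/k)(1−e^(−kτ))]/[p + (1−p)(s/k)(1−e^(−kτ))]. Pairs are for 0.9-year / 3-year medians.

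| On drug at consent | Later starts per year | Drug column starting after consent | Ratio |
|---|---|---|---|
| 50% | 0 | 0% / 0% | 1.00 / 1.00 |
| 50% | 0.05 | 5% / 7% | 0.933 / 0.920 |
| 80% | 0.1 | 2% / 3% | 0.915 / 0.897 |
| 80% | 0.2 | 4% / 6% | 0.841 / 0.807 |
| 50% | 0.2 | 15% / 21% | 0.783 / 0.745 |
| 80% | 0.5 | 8% / 11% | 0.665 / 0.595 |
| 50% | 0.5 | 26% / 34% | 0.598 / 0.531 |
| 30% | 0.5 | 46% / 55% | 0.536 / 0.475 |
| 30% | 1 | 56% / 63% | 0.384 / 0.297 |

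Simulation of the same scenarios (1,000,000 patients each) agrees within 0.01. With a true median of 0.90 year, the displayed medians would be 0.93 against 0.86 (50%, 0.05), 1.01 against 0.76 (50%, 0.2) and 1.23 against 0.42 (30%, 1).

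A different start model leads to the same conclusion. With 25% on drug at consent and a further 25% due to start uniformly over 12 months, the ratio is 0.74 / 0.76. One-year survival is 54% against 40% at the 0.9-year median and 84% against 75% at the 3-year median.

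**Chance with 100 patients** (4,000 simulated studies per scenario). The 95% range of the ratio is 0.49 to 1.23 / 0.38 to 1.54 at 50%, 0.2, and 0.23 to 0.61 / 0.13 to 0.66 at 30%, 1. It includes 1 in 5 of the 8 late-start scenarios at 0.9 years and in 6 of 8 at 3 years.

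**Confounding by severity.** Half the patients are sicker and the overall median is held at 0.9 or 3 years. The formulas are applied to each half and the deaths and times added. The geometric mean start rate is 0.2 per year. In the strong pattern the sicker half has 4 times the death rate, and the half treated more has 4 times the start rate and 70% against 30% on drug at consent. In the milder pattern these are 2.25 times, 2.25 times and 60% against 40%.

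| Pattern | Ratio, any record | Ratio, Visit 1 grouping |
|---|---|---|
| Sicker treated more, strong | 1.403 / 1.383 | 1.709 / 1.681 |
| Sicker treated more, milder | 0.941 / 0.905 | 1.174 / 1.171 |
| Fitter treated more, strong | 0.425 / 0.438 | 0.585 / 0.595 |

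The net ratio can fall on either side of 1. Across 30 simulated combinations of confounding pattern, start rate and median, the any-record ratio was always below the Visit 1 ratio. Within a severity level it was always below 1 (0.33 to 0.96), while Visit 1 grouping gave 0.99 to 1.01.

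**The case against.** The best counter-argument concerns importance, not mechanism.

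- **No comparison is intended.** SAP 8.7 disclaims one, and SAP 11.4 specifies only curves, quartiles and intervals. This stands and limits the harm to a misleading display.
- **The size is unknown.** Patients are enrolled within 6 months of diagnosis, and many users may already be on drug at consent. If all are, the error is zero. This stands, although even 5% to 7% of users starting late gave ratios of 0.93 and 0.92 above.
- **Chance is often larger.** With about 100 patients it usually is. But chance is reflected in the confidence intervals; the grouping error is not.
- **The median contrast depends on poor survival.** At a 3-year median, 64% are alive at Week 100 (0.5^(1.916/3) = 0.642), so the overall median is not reached. The curves would still differ.
- **The fix can move the ratio further from 1.** If sicker patients are treated more, the two errors partly cancel. That is no reason to keep one of them, but it makes the statement on non-comparability essential.
- **The Kaplan-Meier split is inferred.** It follows from the general sentence in SAP 9; SAP 11.4 does not repeat it, and the mock-up tables are not in the documents reviewed. The wording covers all analyses, so the inference is reasonable.
- **The SAP's split may itself be the judgement that Protocol 9.9 calls for.** Possibly, but the SAP does not say so. This is a secondary point.

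**Conclusion.** The concern holds and should be fixed. Followed as written, the plan credits survival before first dose to the drug column whenever a user starts after consent. Taken alone, this favours the drug column: ratios run from 1.00 with no late starts, through about 0.78 / 0.74 in a middle case, to 0.38 / 0.30 at the extreme. These figures rest on exponential survival from consent, the protocol's two medians, no drug effect and assumed start patterns. The sign of the total error is not fixed, because confounding by severity may add to this component or outweigh it.

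The finding is limited to the subgroup display of mortality; whole-population results are not affected. Time to first exacerbation has the same time zero and split, but a patient can start a drug after that event, so its error differs and was not sized here. No claim is made about annual declines.

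**What to change.** For time to death, do not draw Kaplan-Meier curves by any record during follow-up. Choose one of these in the SAP:

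1. **Group by anti-fibrotic use at Visit 1**, stating how use that stopped before baseline is classed; SAP 8.4 leaves this open. This needs SAP wording and one derived variable. Its drawback is that later starters count as no drug at baseline.
2. **Treat use as time-varying from the recorded start date**, so that time before the first dose counts as no drug (delayed-entry curves or person-time rates). This keeps later starters' exposure but needs clean start dates and extra programming. Early risk sets may be small and unstable if few patients are on drug at consent.

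Either way, state in the SAP and beside the display that the change removes immortal time only, that confounding by severity remains, and that the two columns are not a treatment comparison. Reconcile SAP 8.4 and 9 with Protocol 9.9 on when the stratified display will be produced at all. No new data are needed: use at baseline and start and end dates are already collected.
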